## **Participant demographics**

The baseline survey will also include questions on age, body weight, stature, participation in sports and physical activity, previous care, bilateral pain, concomitant conditions (anterior knee pain conditions), symptom duration, health-related behaviors, anthropometrics, pubertal and skeletal maturity, and predicted adult height. Per CONSORT guidelines, we will not perform statistical comparisons of baseline charactistics.

## Study flow and participant timeline {13}

Patients will undergo pre-trial procedures (phone screening, examination, and history, oral and written information, signed consent) before enrollment and treatment start (baseline), which will then last 3 months (13 weeks). A telephone consultation with the treating physiotherapist is planned for month 2 (week 9), that can also result in a clinical visit if needed. Two months (9 weeks) after end-of-treatment, participants will attend the primary clinical follow-up visit at 5 months (22 weeks), followed by the final clinical visit at 8 months. Subsequently, long-term digital-only follow-up will be captured at months 10, 12, 24, and 48. See figure 2 for detailed study-flow, and table 11 for the study schedule.

[figure not shown]

## Sample size considerations {14}

The properties of the primary outcome measure KOOS-child and the "Sport/rec" subscale have been well investigated, with a validation study including adolescent participants with Osgood-Schlatter amongst other overuse- and acute knee disorders. A small cohort of patients in our clinic (n=16) who 1) were eligible for inclusion in the trial at baseline, 2) received the intervention in question and 3) attended follow-up, reported their global rating of improvement on a 7 point Likert scale ranging from 'much worse (7)' to 'much better (1)'. Patients who reported 'much better (1)' or 'better (2)' had a mean improvement on KOOS-child

'Sport/play' subscale of 12.7±16 points, whereas patients reporting less improvement ('little' improvement or 'no change') only had a 3.57 point increase. In absence of more robust specific data in terms of severity, intervention, and length of follow-up, we will utilize this 9 point difference as a threshold for determining superiority. We consider this to be a meaningful change and a relevant between-group difference, and is within the recommended range of 8-10 points (heartbeat-med.com/resources/knee-injury-and- osteoarthritis-outcome-score-koos). This change also exceeds the smallest detectable group-level change (2.66 points) and the standard error of measurement (8.02 points).

In order to detect such a change with a standard deviation of 16 points an  $\alpha$  level (type I/false positive error rate) of 5% and power ( $\beta$ -1, or probability of avoiding type II/false negative error rate) of 90%, 55 (54.8) participants per group would be needed based on an independent one-sided t-test (R 4.0.2, Foundation for Statistical Computing, Vienna, Austria; RStudio 1.0.153, power.t.test package). To account for a potential 15% dropout rate a total of 130 participants will be included.

This will correspond to a 0.56 Cohens d 'medium' effect size at 90% power (figure 3). The smallest effect size reliably detectable will thus be >0.482 (Cohens d 'small' effect size) at  $\geq$ 80% power (Jamovi 1.2.25, jpower module), surpassing the trivial (<0.2) and small (>0.2) effect size thresholds. We also consider this sample size to be operationally feasible within the given timeframe and with the resources available to our group.

## Recruitment {15}

Participants will be recruited through a combination of convenience and consecutive sampling from the uptake area of the Capital Region of Copenhagen, Denmark (1.8M inhabitants), through two different approaches; 1) patients referred to the secondary care specialized outpatient Orthopedic Department at Hvidovre Hospital, and 2) postings to our website encouraging parents of adolescents with anterior knee pain below the knee to contact the study director, which will be also be shared with sports clubs in the uptake area through our organizational network. Based on historical patient flow and past studies in this population, the planned recruitment rate is expected to be around 10-15 participants per month during non-holiday periods. Thus, inclusion is expected to last up to two years, from January 1st 2022 to December 31st 2023.

## **First contact**

Accordingly, all 10-16-year-old patients referred for potential Osgood-Schlatter complaints to the department from other hospitals or general practice, or having contacted the study director themselves, will be screened for eligibility by telephone by the study director before potentially being invited to enrollment visit.

## Assignment of interventions: allocation

## Sequence generation {16a}

Participants will be allocated to either standardized usual care or the experimental intervention with a 1:1 allocation ratio. To perform adequate sequence generation, we will use The Robust Randomization App (RRApp v3.0.1, https://clinicalresearch-apps.shinyapps.io/rrapp/) for a computer-generate sequence in random sized blocks with no stratifications, extracted by a person not otherwise involved in the trial.

## Concealment mechanism {16b}

To conceal allocation and prevent selection bias, the sequence will be implemented using sequentially numbered in sealed opaque envelopes. A person not otherwise involved in the trial will be given the randomization sequence and 65 envelopes containing a paper reading 'group 1' and 65 envelopes containing a paper reading 'group b'. The paper is sandwiched between two black pieces of cardboard, making it impossible to see through even with strong under-lighting. The envelopes have been sealed with glue. They will then order and number the envelopes according to the order from the randomization sequence.

## Implementation of allocation {16c}

During the study period, staff involved in data collection and analysis will be blinded to randomization sequence and block size. Only the personnel responsible for including participants will have the ability to view group allocation, but only after the participant is irreversibly included in the study and have been allocated to their group.

## Assignment of interventions: Blinding

## Who will be blinded {17a}

Outcome assessors and the statistician performing analysis will be blinded in every way to group allocation. To yield valid results from the trial, we will blind intervention-receivers (participants) to treatment allocation and contents of the intervention they are not receiving. This will be done by providing minimal information to participants about the contents of either intervention until after group allocation, nor will they be informed if they are in the experimental (Group A) or usual care group (Group 1). The written and verbal information prior to inclusions will state that the two groups both contain first line treatment modalities such as different advice and exercises, offered as current practice based on the most recent literature.

One reason for not informing participants about the contents of the interventions is that knowledge about the actual content would increase the likelihood of contamination, as participants might want to implement parts of one intervention into the other or vice versa, for example, by doing stretches in addition to the exercises in the experimental group. This would contaminate the experimental intervention leading to a possible underestimation of the efficacy of the intervention in question. Secondly, by keeping participants blinded to treatment allocation, the adverse effects, such as disappointment of not receiving one or the other intervention, could be avoided. This is important because these effects could negatively affect the outcomes, with a risk of an overestimation of the relative efficacy of the intervention in question. This blinding aspect of participants with minimal information about treatment contents will increase the validity of the results. We consider this blinding aspect ethically warranted, as firstly, no current standardized recommendations or best practice of care for Osgood-Schlatter exists, and secondly, there is a considerable variation in the current type and extent of treatment modalities offered for Osgood-Schlatter patients.

To minimize bias (performance- and verification bias), the intervention personnel will not be aware which, if any, of the two treatments is the experimental or the comparator, or if the trial is investigating superiority/non-inferiority/equivalence. Different personnel will deliver each intervention and will not be aware of the contents of the intervention in the opposite arm. However, due to the nature of the interventions, it is required that they are aware of the group allocation of participants in order to deliver their assigned intervention, and they also need to engage participants in conversations about their current pain and symptoms, and their level of physical activity and sports, in order to guide participants through their respective treatments. Blinding intervention personnel to group allocation and some outcomes is therefore not feasible and is not performed, but they will not have access to any data collected by the outcome assessor during clinical testing and ultrasound scanning, nor the patient-reported instruments.

### Procedure for unblinding if needed {17b}

As the study director and the Medical Advisor is unblinded to group allocation, unblinding is not expected to be necessary during the trial.

### **Study personnel**

Intervention personnel will be 6-10 different trained physiotherapists, not be involved in other aspects of the trial. Personnel responsible for doing outcome collection will be 1-2 physiotherapists, not involved in other aspects of the trial and will be blinded to group allocation. Personnel responsible for diagnosis, inclusion, end-of-study visit will be one physiotherapist (KK) and a potential trained replacement, who will not be blinded to either group allocation or outcome measures. The Medical Advisor will be a Chief Orthopedic Surgeon (PH), who will examine participants in need of a second opinion regarding initial diagnosis, AEs, or other sudden health deterioration in participants. A biostatistician (TK) blinded to group allocation in the dataset will perform the analyses.

### **Study training**

The PI has extensive experience delivering the experimental intervention, with all the chosen clinical outcome assessments from previous trials, and clinical work in the target population. In addition, the PI have managed the process of constructing the usual care-intervention through investigation with clinical field experts. Therefore, the PI will train the other physiotherapists in the respective interventions and clinical outcome assessments. All personnel will be trained in the nature of contamination effect and be trained in how to avoid unblinding when engaging participants.

# Data collection and management

## Plans for assessment and collection of outcomes {18a}

Depending on the time point, participants will answer between 85 (baseline) and 38 questions (month 1) in their surveys. In table 11 we have described the schedule of data collection of all outcomes. All outcome data, both clinically obtained by an outcome assessor or patient-reported directly from the participants, will be entered into REDCap. Weekly monitoring will be performed using text-based service (SMS-track®, Esbjerg, Denmark) similarly starting the following Monday after the baseline visit and the following 22 weeks, totaling 23 weekly monitoring questionnaires containing 4-6 questions.

Study phase	Pre-allocation	Baseline	Intervention period				Primary endpoint	Clinical follow-up	Long-term follow-up d
Timepoint		Mo 0	Weekly	Mo 1	Mo 2	Mo 3	Mo 5	Mo 8	Mo 10, 12, 24 48
Enrollment procedures					 	 		•	•
Clinical visit		Х		Х		Х	Х	Х	
At home	Х		Х		Х				Х
Phone screening	Х								
Written information	Х	Х							
Verbal information	X	Х							
Written consent		Х							
Allocation		Х							
Clinical assessments	1								
Clinical examination		Х					Х		
Peak Height Velocity		Х				Х	Х	Х	
Adverse events		Х		Х	Х	Х	Х	Х	
Previous & concomitant treatments		Х		Х	х	Х	Х	Х	
Clinical tests							-		
Pressure-Pain threshold		Х		Х		Х	Х	Х	
Knee extension strength		Х		Х		Х	Х	Х	
Countermovement jump		Х		Х		Х	Х	Х	
Modified Thomas test		Х		Х		Х	Х	Х	
Anterior knee pain provocation test		Х		Х		Х	Х	Х	
Objective longitudinal measures	-ii								
Physical activity (sensors)		•							
Imaging	1								
Ultrasound scanning		Х				Х	Х	Х	
Patient-reported questionnaires									
KOOS-child 4 subscales		Х		Х	х	Х	Х	х	Х
Acceptable Symptom State (PASS)		Х		Х	х	Х	Х	Х	Х
Global rating of change				Х	х	Х	Х	Х	Х
Sport & Physical activity		Х	Х	Х	х	Х	Х	Х	Х
Pain history		Х	Х	Х	х	Х	Х	Х	Х
Self-rated health (EQ-5D-Y)		Х				х	Х	Х	Х
Kinesiophobia (Tampa)		Х				Х	Х		
Therapeutic Alliance (WIA)						х			
Miscellaneous health a		Х							
Pubertal stage (Tanner)		Х				х	Х		
Adherence to treatments			Х	х		х	Х	Х	
Intervention									
Experimental or usual care treatment		—							
Complete self-management		•				.			

## Plans to promote participant retention and complete follow-up (18b)

When capturing electronic questionnaire responses, participants will receive 2 reminders if having not responded and will subsequently be telephoned to ensure responses. We will continue data collection irrespective of adherence to interventions. Data collection will only discontinue if participants explicitly wish to withdraw from the study and not attend further visits. In such cases, we will offer participants the option to only complete electronic patient-reported forms or having treatments delivered by telephone or video chat, however, every reasonable effort will be made to retain all participants and collect all outcomes for every patient enrolled in the study.

## Data management {19}

The study director will manage and curate data in collaboration with the blinded statistician (TK). Sonographs, videos (jump testing requires analyses of high-speed videos), or images (participants might occasionally be asked to send a picture of their knee with painful areas drawn up as part of inclusion or reporting of AEs) will be uploaded to a secure logged server with access restrictions. All other data will be entered directly into REDCap. REDCap users (study personnel) will only have access to their respective relevant instruments and data within the REDCap project to maintain blinding to group allocation, outcomes, and contents of interventions. Written consent forms and other hardcopy data will be stored in locked steel cabinets in a locked room and will be stored for 3 years after completion of the long-term follow-up of the study.

## Data protection & Confidentiality {27,33}

In addition to data captured as outlined, we will keep standard confidential health records and store data in accordance with local laws and healthcare regulations: Our management and storing of data will comply with the articles of General Data Protection Regulation of May 20th 2018, under the EU, Regulation No 2016/679 of the European Parliament and of the Council of 27 April 2016 on the protection of natural persons with regard to the processing of personal data and on the free movement of such data, the Data Protection Act (in Danish: "databeskyttelsesloven") and the Danish Health Care Act (in Danish: "sundhedsloven"). In addition, our plans (and sub-contractors) for use and handling of patient data have been reviewed and approved by the Capital Region Data Protection Agency, Denmark (P-2021-818) after the protocol was approved by the Capital Region Committee on Health Research Ethics, Denmark. Data will only be shared within the study group after unblinding at the pseudo-anonymized level and externally at the fully anonymized level. We plan for only the study director to hold access to the de-identifier key. We only expect to use this prematurely if participants wish to withdraw and have their data irrevocably deleted. As per usual

care, information regarding clinical findings, treatment plans, and delivery, will be noted in the participants regular electronic medical records to support possible post-trial care. No biological material will be obtained.

## Statistical methods

## Statistical methods for primary and secondary outcomes (20a)

Analyses will be performed by a statistician blinded to group allocation and will be performed using (R Foundation for Statistical Computing, Vienna, Austria) in the Rstudio interface (RStudio Team, Boston, USA).

Change scores for KOOS-child 'sport/play' score ( $\triangle$ KOOS) from baseline to month 5 will be calculated for all participants. We will fit a linear regression model using the 'lm' function for  $\triangle$ KOOS-child as the dependent variable and including group allocation as an independent variable. Covariates are described with their measurement, timing and justification in table 12, and will potentially be added to the model.82(p9),215 In order to not introduce unnecessary bias in the model, covariates will however only be included if doing so changes the primary estimate meaningfully, as we expect a equal distribution of these pre-specified covariates given the sample size. Significance level will not determine the inclusion of covariates. The linear model will be evaluated for linearity, multicollinearity, homogeneity of variance, distortion of outliers, homoskedasticity, correlation of variables, distribution of residuals using histograms. If these model assumptions are not met non parametric bootstrap estimation and tests will be used instead. Below we have outlined the intended steps with reproducible R code for Rstudio (version 3.6, 2021.09.0+351)

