#### Step 3: run regression model

[figure not shown]
```
#runs linear regression model with `koos_spor't as the dependent outcome variable
#and `group' as the independent predictor variable. The model is named lm_koos_sp
#`timing' of maturation is included as a covariate.
```

```
lm_koos_sp <- lm(koos_sport~group + timing, data=fu_data)</pre>
```

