## Assumptions for causal mediation analysis

The four assumptions for unconfounded analysis of parsed mediation pathways require 1) no unmeasured exposure-outcome confounders, 2) no unmeasured mediator-outcome confounders, 3) no unmeasured exposure-mediator confounders, 4) no mediator-outcome confounder affected by exposure. Assumption 1 and 3 should be mitigated by randomization and potential covariate adjustment. Because mediators are not randomized it is possible for the mediator-outcome pathway to be confounded (assumption 2 and 4). To address assumption 2, we will include pre-treatment confounders based on available evidence and clinical expertise. This includes potential covariates/moderator variables outline (table 12) and baseline levels of the mediator-variables. Assumption 4 will be addressed by using interventional effects in the mediation analysis along with inclusion of confounders. In addition, to address the assumption of no positivity, that is, a zero risk of any participant exhibiting a positive characteristic of a mediation variable at baseline, all mediator variables with this potential issue, will be change-scores calculated from baseline.

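### The primary model analyses the KOOS-child Sport/play change score without adjusting for its baseline value, which gives up precision and leaves the estimate open to chance baseline imbalance

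*Combined protocol and SAP*

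**What the plan says.** Under Statistical methods for primary and secondary outcomes (20a), the change in Sport/play from baseline to month 5 enters a linear regression "as the dependent variable and including group allocation as an independent variable". On other terms the section says: "Covariates are described with their measurement, timing and justification in table 12, and will potentially be added to the model". It then restricts this: "covariates will however only be included if doing so changes the primary estimate meaningfully". No threshold for a meaningful change is given.

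The moderators/covariates in Table 12 are growth velocity, growth timing, fear of movement, pain intensity, pain frequency, treatment expectations, tibial tubercle maturation and ultrasound severity. Sport/play appears in that table only as the week-22 outcome. The example code in Step 3 is "lm(koos_sport~group + timing, data=fu_data"), with maturation timing as its only covariate.

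The study schedule (Table 11) has KOOS-child completed at month 0. Sequence generation {16a} specifies "random sized blocks with no stratifications". A similar strategy is planned for the other numerical outcomes. The only explicit baseline adjustment is in the mediation section, which adds "baseline levels of the mediator-variables" as confounders.

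**The concern.** Subtracting the baseline is not the same as adjusting for it. A change score fixes the slope of month-5 score on baseline at 1, whereas ANCOVA estimates it. If the true within-arm slope is below 1, as regression to the mean usually makes it, the change score over-corrects and the arm that starts lower by chance appears to gain more. Randomisation balances baseline Sport/play only in expectation, and there is no stratification to limit the imbalance in this one trial.

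The section's reasons for sparing use of covariates do not apply to this one. Linear adjustment for a pre-randomisation measurement introduces no material bias, and the precision gain remains when the arms are well balanced. A rule that admits covariates only if they move the estimate therefore looks at the wrong quantity.

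Precision matters here because Dissemination plans {31a} rests the main conclusion partly on the width of the confidence interval and on the 9-point threshold. Trial status reports recruitment complete at 130 of 130, so further precision can come only from retention and analysis.

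**Working it through.** **Inputs from Sample size considerations {14}.** Difference 9 points ("we will utilize this 9 point difference as a threshold for determining superiority"), SD 16, one-sided alpha 5%, power 90%, dropout 15%, total 130. The SD of 16 is the SD of change scores among improvers in a clinic cohort of 16.

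**Reproducing the plan.** A one-sided two-sample t-test (noncentral t) needs n = 54.82, so 55 per arm, matching the stated 54.8. Then 110/0.85 = 129.4, so 130 in total. Power is 90.1% at 55 per arm and 93.9% at 65 per arm (the plan says up to 94.6%).

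**Assumptions.** The documents do not give the correlation rho between baseline and month-5 scores, or the SDs at the two visits. I take rho from 0.3 to 0.7, first with a common SD s, and hold the SD of change at 16.

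**Variance with equal SDs.**
- Var(change) = 2s²(1 − rho)
- Var(ANCOVA) = s²(1 − rho²)
- Ratio = (1 + rho)/2

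| rho | variance ratio | effective SD = 16√ratio | SE at 55/arm | power at 55/arm | n/arm for 90% |
|---|---|---|---|---|---|
| unadjusted | 1 | 16.0 | 3.05 | 90.1% | 55 |
| 0.3 | 0.65 | 12.9 | 2.46 | 97.7% | 36 |
| 0.5 | 0.75 | 13.9 | 2.64 | 95.9% | 42 |
| 0.7 | 0.85 | 14.8 | 2.81 | 93.8% | 47 |

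The equivalent gain in sample size is 1/ratio − 1: 1/0.65 − 1 = 54% and 1/0.85 − 1 = 18%. The 95% interval half-width at 55 per arm is 1.98 × SE. It falls from 6.0 points to between 4.9 and 5.6.

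**Unequal SDs.** Let month-5 SD be 1.3 times baseline SD. In units of baseline variance, Var(change) = 1 + 1.69 − 2.6·rho and Var(ANCOVA) = 1.69(1 − rho²).

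| rho | Var(change) | Var(ANCOVA) | saving | power at 55/arm |
|---|---|---|---|---|
| 0.3 | 1.910 | 1.538 | 20% | 94.8% |
| 0.5 | 1.390 | 1.268 | 9% | 92.3% |
| 0.7 | 0.870 | 0.862 | 1% | 90.3% |

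In general, Var(change) − Var(ANCOVA) = (SD_baseline − rho × SD_month 5)². This cannot be negative, so the most that adjustment can lose is about one degree of freedom.

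**Chance imbalance.** With equal SDs, a baseline difference D shifts the change-score contrast by (1 − rho) × D against the arm that starts higher. At rho = 0.5 the baseline SD is 16/√(2 × 0.5) = 16. A 1-SE imbalance at 65 per arm is 16√(2/65) = 2.8 points, which shifts the estimate by 1.4. At 55 per arm, an imbalance at the 1.96-SE limit is about 6.0 points and shifts it by about 3.0. For rho 0.3 and 0.7 the shift at that limit is 3.5 and 2.3 points.

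**Attrition.** Table 3 reports pilot dropout of 3/15, or 20%. If that held overall, 130 × 0.80 = 104, or 52 per arm. Power would be 88.6% unadjusted and 92.6% to 97.1% adjusted (rho 0.7 to 0.3, equal SDs).

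**The case against.** The strongest reply is that this is a preference for efficiency, not an error. Over repeated randomisations the change-score contrast is unbiased and its interval has correct coverage. The plan is coherent too: the hypothesis, the SD and the model all concern change, and the sample size reproduces. All of that stands, and it limits how serious the point is.

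Four further objections have some force:

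- **One source, two descriptions.** Lost precision and conditional bias from imbalance come from the same place. The unadjusted SE already includes variation due to baseline imbalance, and the 1.4-point shift is about half of that SE. The two should not be counted as separate harms.
- **The size is uncertain.** Eligibility selects adolescents with markedly reduced participation or severe pain, so scores may spread out as some recover and others do not. With a widening SD the gain shrinks, as shown above. With a narrowing SD it grows.
- **The attrition argument is thin.** Three of 15 has an exact 95% interval of roughly 4% to 48%, and it met the pilot's own limit. Multiple imputation is also planned for missing data.
- **Baseline data are not ignored.** Mixed-effects models that include month 0 are planned, and baseline pain intensity and frequency are candidate covariates. But the section on additional analyses lists mixed-effects models among the sensitivity analyses. The pain items are at best partial proxies and enter only through the change-in-estimate rule. Imputation fills missing values but leaves the primary model unadjusted. None of these repairs the primary estimate.

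The code is labelled an example and its printed output is plainly not on a 0–100 scale, so it is supporting evidence only. The text and Table 12 carry the point.

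**Conclusion.** The concern holds. The primary model omits the baseline value of its own outcome, and no route in the plan admits it. Adjustment would reduce the variance of the treatment effect by 15% to 35% if the two visits have equal SDs and rho lies between 0.7 and 0.3. The saving is 1% to 20% if month-5 SD is 1.3 times baseline. The direction is certain apart from one degree of freedom; the size rests on assumed values that the documents do not supply. The planned analysis is valid and meets its power target on its own inputs, so this is a change that should be made rather than one without which the trial fails.

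**What to change.** Before unblinding, specify the primary model as month-5 Sport/play, or its change, regressed on group and baseline Sport/play. Baseline should always be included and be exempt from the change-in-estimate rule. With baseline in the model the group estimate is the same for either outcome, so the hypothesis about change need not be reworded. Apply the same rule to other numerical outcomes that have a baseline value; global rating of change has none. Update the example code to lm(koos_m5 ~ group + koos_m0 + ...), and keep the unadjusted change-score comparison as a sensitivity analysis.

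No new data are needed. The statistical cost is one degree of freedom. The administrative cost is one model term and one sentence in the analysis plan, plus a report to the review board and a justification in the main report, as the section on protocol amendments requires.
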